#### 2.5 Study Design

This is a non-randomized prospective trial. Patients who are referred to Nuclear Medicine for evaluation of extent of cancer and are scheduled to undergo the F FDG or Ga DOTA TATE PET/CT will be asked to have the scan repeated on the same day using PET/MRI scanner. There will be a single injection of F FDG or Ga DOTA TATE followed by the PET/CT scan and immediately after by the PET/MRI scan. There will be no additional radiation to the patient. This is because only one injection of F FDG or Ga DOTA TATE will be given and the MRI uses non-ionizing radiation.

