#### 5.2 Details of Imaging (i.e. dynamic, static, number of scans, etc.)

Whole-body (skull base to mid-thighs) PET/CT images will be obtained using the GE PET/CT 600 and 690 scanners (GE Healthcare) per standard oncologic protocols (7). In brief, PET/CT images will be acquired in 3D mode at 45-60 minutes after injection of 10-12 mCi of F FDG or 5-7 mCi of Ga DOTA TATE. The PET emission scan is corrected using segmented attenuation data of the CT scan. The PET images are reconstructed with a standard iterative algorithm (OSEM, two iterative steps, 28 subsets) using GE software release 5.0. All images are reformatted into axial, coronal, and sagittal views and viewed with the software provided by the manufacturer (AW, GE Medical Systems).

Immediately after completion of the PET/CT exam, the patients will be transferred to the PET/MRI suite at the Lucas Imaging Center and undergo the PET/MRI image acquisition with the least delay. Acquisition will start in the pelvic region and move toward the head. First, a localizer MRI scan will be performed to define the table positions. After correct positioning of the spatial acquisition windows will be ensured, the combined PET/MRI acquisition will be initiated with 3-5 table positions at a 4-min acquisition time per table position. First, a coronal 2-point Dixon 3-dimensional volumetric interpolated breath-hold T1weighted MRI sequence will be acquired at each table position and used for the generation of attenuation maps and for anatomic allocation of the PET results. Simultaneously with the start of the Dixon MRI sequence, the PET acquisition will start at the same table position, thus ensuring optimal temporal and regional correspondence between MRI and PET data. The PET acquisition time will be 4 min per table position, taking delayed acquisition times and radioactive decay into account. After completion of the PET acquisition, the table will be moved to the next table position and the procedure will be repeated. In the thorax and abdomen regions, the MRI scans will be acquired during breath-hold in shallow inspiration, similarly to the acquisition of the low-dose CT (8). Other sequences may also be used as needed (9). Multiplanar pre- and post-contrast MR images may be obtained at multiple stations as needed. Images will be reformatted into axial, coronal, and sagittal views and viewed with the software provided by the manufacturer (AW, GE Medical Systems).

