#### 10. MEASUREMENTS

#### **10.1 Primary outcome measure**

We will evaluate the maximum standardized uptake value (SUVmax) of F FDG or Ga DOTA TATE in the lesions detected with both scanners. There are now several papers based on other vendors' scanners (no GE PET/MRI scanner built yet). The authors showed that in oncologic patients examined with PET/CT and PET/MRI, the SUVmax values generally correlate well in normal organ tissues. SUVmax derived from PET/MRI can be used reliably in clinical routine. Differences observed between MRI and CT derived SUV values may be attributed to the time-delay between the PET/CT and PET/MRI scans or biologic clearance of radiotracer (*10, 11*).

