#### 11.5. **Primary Analysis**

#### 11.1.1. Analysis Population

Analysis population: all lesions identified by either modality (per-lesion analysis).

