#### 11.1.2. Analysis Plan

Normal quantile plots of  $SUV_{max}$  for each scanner will be prepared to assess to what extent the distribution can be approximated by the normal distribution, and to suggest a suitable transformation if not. The distribution of  $SUV_{max}$  for each scanner will be summarized with means, standard deviations, range, median and upper and lower quartiles. The distribution of the difference ( $SUV_{max}$ \_PET/CT –  $SUV_{max}$ \_PET/MRI) (difference of transformed values if applicable) will likewise be summarized. Cumulative distribution (waterfall plots) may be prepared to assist in the evaluation of the results. Patient clinical and demographic characteristics will be summarized using relevant summaries (proportions for categorical variables, means and standard deviations for continuous variables.

The mean difference plus or minus twice the standard deviation of the difference will be calculated as a measure of absolute accuracy. The relative accuracy will be calculated by dividing the preceding interval by the arithmetic average of the mean  $SUV_{max}$  of the two scanners. The interpretation of these intervals is that we can expect that approximately 95% of future differences to lie in these intervals. A paired t-test will be used to aid in the interpretation of the results. Sensitivity analyses may be conducted using linear mixed effects models to account for possible clustering of lesions within patients.

The difference of  $SUV_{max}$  measures will be correlated with patient and lesion characteristics and with time after injection using the appropriate method (Pearson correlation for continuous variables such as age and time from injection, two-sample t-tests for binary attributes (sex) and analysis of variance for categorical variables).

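### The paired t-test treats lesions as independent, and the model for lesions clustered within patients is only optional

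*Combined protocol and SAP*

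**What the plan says.** Section 11.1.1 sets the unit of the primary analysis: "Analysis population: all lesions identified by either modality (per-lesion analysis". It places no cap on lesions per patient.

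Section 11.1.2 has three relevant parts:

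- **Main summary:** "The mean difference plus or minus twice the standard deviation of the difference will be calculated as a measure of absolute accuracy".
- **Test of the mean difference:** "A paired t-test will be used to aid in the interpretation of the results". This is the only test of the mean difference in the plan. Its unit is not restated, but it follows from the per-lesion population.
- **Clustering:** "Sensitivity analyses may be conducted using linear mixed effects models to account for possible clustering of lesions within patients".

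The same section relates the difference to patient and lesion characteristics: "Pearson correlation for continuous variables such as age and time from injection, two-sample t-tests for binary attributes (sex", with analysis of variance for categorical variables. Clustering is not mentioned for these tests.

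The sample size in section 11.6 is expressed in subjects. It contains no lesion count, ICC or design effect.

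**The concern.** The analysis that assumes independent lesions is definite; the one that respects the data structure is discretionary.

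Lesions in one patient are unlikely to give independent differences. Section 2.5 describes one injection "followed by the PET/CT scan and immediately after by the PET/MRI scan", so those lesions share most of the delay between scans. Section 10.1 names that delay as a source of discrepancy: "Differences observed between MRI and CT derived SUV values may be attributed to the time-delay between the PET/CT and PET/MRI scans". To the extent that the delay varies from patient to patient, it makes differences within a patient alike. Tracer (section 4.1) and PET/CT model (section 5.2) can also differ between patients while being common to one patient's lesions. The correlation is not complete, because the delay also varies by body region: "Acquisition will start in the pelvic region and move toward the head".

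With positive correlation and more than one lesion in some patients, the t-test's standard error is too small. A reader who uses the p-value as the plan intends could take chance for a scanner effect. Age and sex are constant within a patient, so lesion-level tests against them count the same patient several times and could suggest a dependence that is not there.

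**Working it through.** **1. Inputs.** From the documents: 100 patients (section 11.7); CV 0.38 and correlations 0.5 and 0.9 (section 11.6); lesion as unit (section 11.1.1). Not in the documents, so assumed: two-sided alpha 0.05, m = 1 to 10 lesions per patient, ICC of the lesion differences 0.1 to 0.5.

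**2. The plan's own figures.** With one independent difference per subject on the log scale, SD_diff = 0.38 × √(2(1 − ρ)), and the detectable relative difference is exp((1.960 + 0.842) × SD_diff/√n) − 1.

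- n = 200, ρ = 0.5: SD_diff = 0.38; exp(2.802 × 0.38/√200) − 1 = 7.8% (stated 8%).
- n = 200, ρ = 0.9: SD_diff = 0.170; result 3.4% (stated 3.4%).
- n = 100, ρ = 0.5: exp(2.802 × 0.38/10) − 1 = 11.2% (stated 11%).

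The power statement therefore rests on independent patients, while the test runs on lesions.

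**3. Real error of the lesion-level t-test, equal counts.** The design effect is DE = 1 + (m − 1) × ICC. The t-test understates the standard error by a factor √DE, so its real error is 2 × (1 − Φ(1.96/√DE)). For m = 3 and ICC 0.3, DE = 1.6, √DE = 1.265, and 2 × (1 − Φ(1.55)) = 12.1%.

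| Lesions per patient | ICC 0.1 | ICC 0.3 | ICC 0.5 |
|---|---|---|---|
| 1 | 5.0% | 5.0% | 5.0% |
| 2 | 6.2% | 8.6% | 11.0% |
| 3 | 7.4% | 12.1% | 16.6% |
| 5 | 9.8% | 18.6% | 25.8% |
| 10 | 15.5% | 30.8% | 40.3% |

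Simulation agrees: 12.2% for m = 3, ICC 0.3.

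**4. Unequal counts.** Simulated under no difference, with 100 patients, geometric lesion counts capped at 20, ICC 0.1 to 0.5 and 4,000–5,000 replicates per cell, the lesion-level t-test rejected in 7.8–16.1% (mean 2 lesions), 9.7–25.3% (mean 3) and 13.0–37.1% (mean 5). A separate simulation with uncapped geometric counts gave 18.1% for mean 3, ICC 0.3.

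**5. Age and sex tests.** With equal counts, the lesion-level sex t-test and age correlation rejected in 5.7–11.1% (m = 2), 7.6–16.2% (m = 3) and 9.2–26.6% (m = 5).

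**6. Methods that respect clustering.** Over the 18 cells (equal and geometric counts), a mixed model with a random patient intercept (REML, t with 99 df) rejected in 4.4–5.6%, and the per-lesion mean with a patient-clustered standard error in 4.5–5.8%. In the separate simulation, a t-test on patient means stayed at 4.6–5.3%.

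**7. What is not affected.** The mean ± 2 SD limits contain no standard error. The pooled SD was 0.994–0.999 of the true SD, and coverage was 95.1–95.4% in every scenario. For m of 2, 3 or 5 and ICC up to 0.5, the effective number of independent lesions, 100m/DE, is at least 200/1.5 = 133. That exceeds the 100 subjects of the sample size, so clustering costs no power against it.

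**The case against.** - **The plan already anticipates clustering and names the right model.** It does, and this makes the fix easy. An optional sensitivity analysis still does not correct a definite test, and it leaves the choice to be made after the results are seen.
- **The t-test decides nothing.** No alpha, hypothesis or success rule is attached to it; the main result is the mean ± 2 SD. This stands, and it limits the harm to a misleading p-value. It is nevertheless the only test of the mean difference, and the sample size is justified by power to detect such a difference.
- **A shared delay produces correlation only as far as it varies between patients.** This is right: a uniform delay would shift the mean and add nothing to the ICC, and an error in administered activity would largely cancel in a log ratio. The documents do not give the spread of delays. Some positive correlation remains plausible because delay, tracer and PET/CT model can all differ between patients.
- **The size is assumed.** This stands. The percentages are illustrative, and the highest simulated rate, 37.1%, needs ICC 0.5, a mean of 5 lesions and skewed counts together.
- **Fewer lesions may enter the test.** Section 10.1 speaks of lesions seen on both scanners and section 11.1.1 of lesions seen on either. A paired difference needs both values, which may lower m but does not remove the clustering.

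**Conclusion.** The concern holds and should be fixed. As written, the plan commits to tests that treat lesions as independent and leaves the correction to discretion. At an assumed two-sided 0.05 and ICC 0.1 to 0.5, the paired t-test's false-positive rate is 6–11%, 7–17% or 10–26% for 2, 3 or 5 lesions per patient, and 8–16%, 10–25% or 13–37% for the same means with skewed counts. The age and sex tests behave alike. There is no inflation with one lesion per patient or an ICC of zero.

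That the plan is worded this way is certain; how large the inflation will be is not, because neither the lesion count nor the ICC is in the documents. The error can suggest a scanner difference that does not exist. It does not support a false claim of equivalence, and the ± 2 SD limits can stay.

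**What to change.** In section 11.1.2:

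1. Make the planned analysis a linear mixed model of the within-lesion difference (or log ratio) with a random patient intercept, and report the mean difference with its 95% confidence interval.
2. Make the lesion-level paired t-test the sensitivity analysis.
3. Use the same random patient intercept when relating differences to age, sex, time from injection and other characteristics.
4. Keep the mean ± 2 SD limits as planned.

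If the equally weighted per-lesion mean implied by section 11.1.1 must be kept exactly, use that mean with a patient-clustered standard error instead; the two methods controlled the error about equally well in simulation. Section 10.4 has two physicians read all scans independently. If both readings enter the analysis, a patient intercept alone does not cover repeated readings of one lesion, so the text should say how they are combined.

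The cost is a few sentences and slightly more analysis work; no new data are needed. The interval for the mean difference will be wider. With unequal lesion counts, the mixed-model mean gives patients with many lesions less weight than the plain per-lesion mean does.

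### The planned covariate tests in 11.1.2 can show what shifts the centre of the mean ± 2 SD interval, but not what changes only its width

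*Combined protocol and SAP*

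**What the plan says.** Under the primary analysis (11.1.2 Analysis Plan), the agreement result is an interval: "The mean difference plus or minus twice the standard deviation of the difference will be calculated as a measure of absolute accuracy". Its stated meaning is that "we can expect that approximately 95% of future differences to lie in these intervals". The test of mean bias is secondary to this: "A paired t-test will be used to aid in the interpretation of the results".

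The last paragraph of 11.1.2 turns to covariates. The PET/CT minus PET/MRI difference "measures will be correlated with patient and lesion characteristics and with time after injection using the appropriate method". The methods named are "Pearson correlation for continuous variables such as age and time from injection", with "two-sample t-tests for binary attributes (sex) and analysis of variance for categorical variables".

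Nothing else in the document looks at spread by factor. Section 11.4 only points forward. The distribution summaries and waterfall plots in 11.1.2 are overall. The mixed models are optional and serve another purpose: "Sensitivity analyses may be conducted using linear mixed effects models to account for possible clustering of lesions within patients". The analysis population (11.1.1) is all lesions, per lesion.

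**The concern.** The width of the agreement interval comes from the SD of the differences, whereas the covariate tests compare only means of the signed difference. A factor that makes the scanners disagree more in both directions leaves that mean where it was, and the planned tests have nothing to find.

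Unequal spread is a reasonable thing to check here. The study pools two tracers, two PET/CT scanners and patients with any cancer, and the interval between scans is not fixed. If spread does differ, one pooled interval would be quoted for lesions to which it does not apply. A row of non-significant covariate tests could then be taken as support for using it everywhere.

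**Working it through.** **Step 1. The plan's own figures (11.6).** Inputs: CV 0.38 for both scanners, correlation 0.5 or 0.9 on the log scale, 80% power. Two-sided alpha of 0.05 is my assumption, as none is stated. SD of the log difference = 0.38 × √(2(1 − ρ)), which is 0.38 at ρ = 0.5 and 0.170 at ρ = 0.9. Detectable difference = exp[(1.960 + 0.842) × SD/√n] − 1:

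- n = 200, ρ = 0.5: exp(0.0753) − 1 = 7.8% (stated 8%)
- n = 200, ρ = 0.9: exp(0.0337) − 1 = 3.4% (stated 3.4%)
- n = 100, ρ = 0.5: exp(0.1065) − 1 = 11.2% (stated 11%)

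The figures reproduce. The sample size, too, concerns a mean shift only.

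**Step 2. What the planned tests can detect.** Let d be the difference and x a covariate. If the mean of d is the same at every x and only its SD varies, then Cov(x, d) = 0 and all group means are equal. The null hypothesis of each planned test is true, so each rejects at about its nominal rate.

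**Step 3. Size for a two-level factor.** Assumptions: two equal groups with the same mean, 100 independent lesions, and group SDs chosen so that the pooled SD is about 0.17, for example √((0.10² + 0.22²)/2) = 0.171. The pooled limits are then ±0.34, or −29% to +40% when back-transformed. Coverage in a group is 2Φ(0.34/SD) − 1. The spread test is Brown-Forsythe. Rejection rates are from simulation.

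| Group SDs | Coverage of ±0.34 | Average coverage | Planned t-test | Spread test |
|---|---|---|---|---|
| 0.10 / 0.22 | 99.9% / 87.8% | 93.9% | 5% | >99% |
| 0.13 / 0.202 | 99.1% / 90.8% | 94.9% | 5% | 78% |
| 0.15 / 0.188 | 97.7% / 92.9% | 95.3% | 5% | about 30% |

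In the first row the groups' own limits are exp(±0.20), or −18% to +22%, and exp(±0.44), or −36% to +55%. With 60 lesions the spread test falls to about 54% in the second row and 17% in the third. Coverage and power depend on the ratio of the SDs, so taking ρ = 0.5 instead of 0.9 changes only the limits: the pooled half-width becomes 2 × 0.38 = 0.76.

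The 5% assumes equal groups. With an 80/20 split and an SD ratio of 2, an equal-variance t-test rejects 18% of the time if the smaller group is the more variable, and 0.5% if the larger group is. The Welch version stays at 5%. A rejection of this kind would be read as a mean shift.

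**Step 4. Size for delay.** Assume the SD rises linearly from 0.08 to 0.25 over the range of delays, with n = 100. With no mean trend, Pearson correlation flags delay about 5 to 6% of the time on the signed difference and about 96% on the absolute deviation. If the mean log difference also drifts over that range, the planned test gains power: 13% for a drift of 0.05, 37% for 0.10, 70% for 0.15 and 90% for 0.20. These drifts are assumptions.

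**Step 5. Clustering.** With 4 lesions per patient and an intraclass correlation of 0.3 to 0.5 (assumed), a Brown-Forsythe test that ignores patients rejects about 7 to 12% of the time for a patient-level factor when spread does not differ at all. A spread test therefore needs the clustering built in.

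**The case against.** Four points stand against a stronger reading.

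- A reader might infer that the covariate analysis is wrong. It is not. What shifts the bias is a proper question, the mean difference is the centre of the primary interval, and the named tests address it.
- A reader might infer that the pooled interval fails. The 95% in 11.1.2 is a statement about future differences overall, and average coverage stays between 93.9% and 95.3% in every case in the table.
- A reader might infer that the plan will declare agreement independent of delay or lesion type. The text makes no such claim and attaches no decision rule to these tests.
- The delay example is weaker than it looks. Section 10.1 says "Differences observed between MRI and CT derived SUV values may be attributed to the time-delay between the PET/CT and PET/MRI scans" or to tracer clearance, and says nothing about spread. PET/CT always comes first, so such an effect may also move the mean, which Pearson correlation does target.

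It is also fair to say that the SDs are invented for illustration, and that the spread test is reliable only when heterogeneity is large. What remains is narrower: no planned analysis addresses whether the width of the interval depends on any factor. A transformation chosen from the quantile plots might even out the variance against SUV level, but it would not test tracer, lesion type or delay.

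**Conclusion.** The point holds as a gap in a supportive analysis, not as an error in the primary one. The planned tests can identify factors that shift bias. For a factor that changes only the spread, they have little or no power beyond the nominal error rate, about 5% in equal groups.

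The consequence depends on heterogeneity that the documents do not quantify. For assumed SDs of 0.10 and 0.22, the pooled limits cover 99.9% of one group and 88% of the other. For 0.15 and 0.188 they cover 98% and 93%, a small departure that even a spread test would usually miss at n = 100. The rejection rates assume independent lesions and normal log differences with, unless a drift is stated, no mean shift. The addition is worthwhile because it is cheap; no stated figure has to be withdrawn.

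**What to change.** Keep the planned tests. Add to the last paragraph of 11.1.2 that, for the same covariates and on the scale used for the limits, the absolute residual |difference − fitted mean| will be regressed on each covariate, with a patient random effect or patient-clustered standard errors. Specify this directly: the named covariate tests make no allowance for clustering, and the mixed models in 11.1.2 are optional.

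Report mean ± 2 SD by tracer, and by any factor with a material change in spread (as a function of it, for time), beside the pooled interval.

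The cost is a sentence or two in the plan and a second pass over data already collected, with no new patients or scans. The downside is more tests without multiplicity control, so they should be labelled exploratory. A null result should not be read as evidence of constant spread, given the limited power for mild differences.

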#### 11.6. Sample Size

Data from Kershah (*10*) shows coefficients of variation between SUV measurements between PET/CT and PET/MRI ranging from 0.21 to 0.51, about 0.33 for CT attenuation correction and 0.38 for MR attenuation correction. We present calculations assuming a CV of 0.38 for both modalities and a Pearson correlation of 0.5 (moderate scenario) and 0.9 (optimistic scenario). Assuming a Pearson correlation of 0.5 on the log scale, 200 subjects provide 80% power to detect a relative difference of 8% between the SUVmax values using the two modalities. With an optimistic assumption of a Pearson correlation of 0.9, 200 patients provide 80% power to detect a relative difference of 3.4%. These differences do not seem minute, they will be a bit larger with only 100 subjects: assuming a Pearson correlation of 0.5 on the log scale, 100 subjects provides 80% power to detect a relative difference of 11% between the SUVmax values using the two modalities. With an optimistic assumption of a Pearson correlation of 0.5 on the log scale, 100 subjects provides 80% power to detect a relative difference of 11% between the SUVmax values using the two modalities. With an optimistic assumption of a Pearson correlation of 0.9, 200 patients provide 80% power to detect a relative difference of 5%.

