#### 1. OBJECTIVES

#### 1.1 Primary Objective

 To evaluate if PET/CT and PET/MRI scanners provide equivalent results for evaluation of cancer patients

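### Section 11.6 gives power to detect a mean log difference, which describes neither the agreement interval in 11.1.2 nor the power to support equivalence

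*Combined protocol and SAP*

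**What the plan says.** The primary objective (1.1) is to find out whether the two scanners "provide equivalent results for evaluation of cancer patients".

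The analysis plan (11.1.2, under 11.5) states: "The mean difference plus or minus twice the standard deviation of the difference will be calculated as a measure of absolute accuracy". A relative version divides that interval by the average of the two scanners' means. Both are read as covering about 95% of future differences. The test has a supporting role: "A paired t-test will be used to aid in the interpretation of the results". The difference is taken on untransformed SUVmax unless the normal quantile plots suggest a transformation.

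The sample size section (11.6) sets its inputs as follows: "We present calculations assuming a CV of 0.38 for both modalities and a Pearson correlation of 0.5 (moderate scenario) and 0.9 (optimistic scenario"). It then gives four detectable differences, all at 80% power:
- "200 subjects provide 80% power to detect a relative difference of 8% between the" two modalities (correlation 0.5).
- "With an optimistic assumption of a Pearson correlation of 0.9, 200 patients provide 80% power to detect a relative difference of 3.4" per cent.
- "100 subjects provides 80% power to detect a relative difference of 11% between the" modalities (correlation 0.5).
- "With an optimistic assumption of a Pearson correlation of 0.9, 200 patients provide 80% power to detect a relative difference of 5" per cent.

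Expected accrual in 11.7 is 100 patients. The documents state no significance level for 11.6, no equivalence margin, no acceptable interval width, no expected interval and no precision target for its limits.

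**The concern.** Power to detect a difference is the chance of declaring the scanners different when their means differ by the stated amount. The objective asks for the opposite kind of conclusion. The measure chosen to describe agreement, the mean ± 2 SD interval, is not mentioned in 11.6 at all.

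Two consequences follow. First, someone reading 8%, 3.4%, 11% or 5% could take these as the resolution of the agreement assessment. They concern only the mean difference. The spread of individual differences, which sets the width of the interval, is far larger and is not reduced by enrolling more patients. Second, a non-significant t-test could be read as support for equivalence, although 11.6 gives no power for that conclusion.

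The scales also differ. The power figures are on the log scale, while the default test in 11.1.2 is on raw SUVmax, so the stated 80% does not carry over directly.

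**Working it through.** **Inputs.** From 11.6: CV 0.38 for each scanner, correlation ρ of 0.5 or 0.9, power 80%. From 11.7: N = 100. Assumptions: two-sided 5% significance; CV used directly as the log SD; one independent pair per patient; zero mean difference for the expected interval.

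**1. SD of the paired log difference.** SD = 0.38 × √(2(1−ρ)), which is 0.380 at ρ = 0.5 and 0.170 at ρ = 0.9.

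**2. Reproducing 11.6.** Detectable difference = exp[(1.960 + 0.842) × SD/√n] − 1.

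| n | ρ | Exponent | Result | 11.6 |
|---|---|---|---|---|
| 200 | 0.5 | 0.0753 | 7.8% | 8% |
| 200 | 0.9 | 0.0337 | 3.4% | 3.4% |
| 100 | 0.5 | 0.1065 | 11.2% | 11% |
| 100 | 0.9 | 0.0476 | 4.9% | 5%, printed with 200 patients |

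One-sided 5% gives 6.9%, 3.0%, 9.9% and 4.3%, which do not match. A log SD of √ln(1 + 0.38²) = 0.367 turns the 3.4% into 3.3%, so 0.38 appears to have been used directly. The figures are therefore those of a two-sided 5% paired test for a difference in mean log SUVmax. The last one fits 100 patients; with 200, power at 5% would be about 98%.

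**3. Expected agreement interval from the same inputs.**
- Log scale, as a ratio: exp(±2 × 0.380) = 0.47 to 2.14 at ρ = 0.5; exp(±2 × 0.170) = 0.71 to 1.40 at ρ = 0.9.
- Relative formula of 11.1.2 on untransformed values, equal means: ±2 × 0.38 × √(2(1−ρ)) = ±76% or ±34%.

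The sample size n does not enter either expression.

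**4. What N does govern: the precision of each limit.** The standard error of a limit is SD × √(1/n + 4/(2(n−1))). At n = 100 this is SD × √(0.0100 + 0.0202) = 0.174 SD. Multiplying by t = 1.984 gives a 95% CI half-width of 0.345 SD. The upper limit is then 2.14 (1.88 to 2.44) at ρ = 0.5, or 1.40 (1.32 to 1.49) at ρ = 0.9. These CIs hold for one pair per patient. The analysis is per lesion, and clustering would change them.

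**5. Power on the raw scale.** I simulated lognormal pairs with log SD 0.38 and n = 100, and tested the raw difference with a two-sided 5% paired t-test. Power is about 72–74% at an 11% difference (ρ = 0.5) and about 76% at 5% (ρ = 0.9). The log-scale test at the same rounded differences has about 77–78% and 81–82%.

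**6. Mean-ratio bounds that N = 100 supports.** For two one-sided 5% tests with 80% power at a true ratio of 1, solve 2Φ(b/SE − 1.645) − 1 = 0.80. This gives b = (1.645 + 1.282) × SE.
- ρ = 0.5: SE = 0.380/10 = 0.0380, b = 0.111, ratio bounds 0.895 to 1.118.
- ρ = 0.9: SE = 0.0170, b = 0.0497, ratio bounds 0.951 to 1.051.

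**The case against.** The strongest reply is that nothing here shows the trial to be the wrong size. The interval is prespecified, will be reported whatever 11.6 says, and is already described as covering about 95% of future differences. Its width does not depend on N. A systematic difference is one component of agreement, so power for the mean is incomplete rather than irrelevant. Section 11.6 also states its CV, its correlations and that the power is for detection. All of this stands, and it makes the matter one of correct description, not of an unsound design.

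Four stronger readings are tempting and should be resisted.

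- *That the plan will report −53% to +114%, or −29% to +40%.* Those are the log-scale ratios expressed as percentages. The default in 11.1.2 is untransformed, where the same inputs give ±76% and ±34%. They are also outer limits under an assumed correlation, not typical disagreement.
- *That equivalence power falls well short of 80%.* The documents give no margin, so the answer depends on the bounds chosen. With bounds of 1/1.11 to 1.11 and 1/1.05 to 1.05, two one-sided 5% tests have 73% and 78% power at a true ratio of 1. With literal ±11% and ±5%, they have about 79% and 81%.
- *That the bounds in step 6 are an equivalence margin.* They are worked back from N. An acceptability margin has to come from what difference matters, and the documents do not supply it.
- *That these intervals predict the lesion results.* The cited CVs come from a study of normal structures, so the spread in lesions could differ.

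**Conclusion.** The point holds and should be fixed. Section 11.6 answers whether a mean difference in log SUVmax would be detected. The objective is equivalence, and the stated measure of agreement is the mean ± 2 SD interval. The detection figures are numerically sound, apart from the patient number printed with the 5% figure, but they should not be read as the resolution of the agreement assessment. Under the plan's own inputs the individual differences are expected to span a ratio of 0.47–2.14 or 0.71–1.40, against mean differences of 11% and 5%. On the default raw scale the test falls roughly 4 to 8 points short of the stated 80%. At 11%, part of that shortfall is rounding, since the log-scale test itself has 77–78% there.

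These sizes rest on the assumptions listed in the working: a log SD of 0.38, two-sided 5%, no mean difference for the interval, and one independent pair per patient. The mismatch between the sample size section and the objective depends on none of them. The documents do not support the inference that 100 patients is too few.

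**What to change.** 1. In 11.1.2, prespecify the log ratio as the scale for both the paired test and the limits of agreement, so that the power figures apply to the test that is run.
2. In 11.6, label the existing figures as power to detect a mean log difference, not power for equivalence. Reconcile the 5% figure, which fits 100 patients and is printed with 200. Also reconcile the repeated 11% sentence, which is called optimistic but uses correlation 0.5.
3. In 11.6, state for N = 100 the expected limits in each scenario (ratio 0.47–2.14 and 0.71–1.40) and their precision: a 95% CI half-width of about 0.34 SD for one pair per patient, with a note that clustered lesions will change it.
4. State that 80% power for two one-sided 5% tests at a true ratio of 1 needs ratio bounds of about 0.895–1.118 (ρ = 0.5) or 0.951–1.051 (ρ = 0.9). Say plainly that this describes what N = 100 supports and is not a clinical margin.

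The cost is a rewording of 11.6 and a sentence in 11.1.2. Enrolment and measurements do not change. The downside is that the stated figures will look less favourable.
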